### Methods

Clinical patient evaluation was assessed by using the HHS and WOMAC score at the minimum follow-up of 10 years.

Radiological evaluation was assessed using Moore's criteria regarding osseointegration (radial trabeculae, superior and inferior buttresses, stress shielding, absence of radiolucent lines). Adequate osseointegration of the cup: at least 3 parameters out of 5.

A prosthetic implants survival rate evaluation has been made using Kaplan-Meier method.

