### **Study description**

Total hip arthroplasty (THA) is the recommended treatment to restore functionality and control pain in post-traumatic hip osteoarthritis due to acetabular fractures. However, THA in post-traumatic osteoarthritis following acetabular fractures is a complex procedure and it is burdened with occasional failures. Modest long-term outcomes have been reported, generally lower than conventional THAs performed due to osteonecrosis or primary osteoarthritis: 10-year clinical results are usually good but not excellent (average Harris Hip score: 88), 10-year revision rate is between 15% and 26%. In review study about the complications of post-traumatic THAs, 30% of ossifications, 4.4% of dislocations, 5.6% of infections, and 2.1% of neurovascular lesions were reported: all the percentages were higher than in primary conventional THAs.

The most critical issues are related to the young age of the patients, to the anatomical changes affecting the periarticular tissues, to the presence of hardware and to the greater exposure to septic complications. All these factors may prevent the surgeon to achieve a good cup positioning and a satisfying outcome. However a correct surgical technique, associated with meticulous pre-operative planning and the use of low-wear implants can improve the clinical result and the long term survival rates.

However, the literature about mid-to-long-term studies about post-traumatic THAs is scarce (currently 5 with an average follow-up of at least 5 years). Furthermore, these studies often include outdated implants, positioned with invasive surgical techniques and with removal of all previous hardware. Therefore, a long-term study (minimum 10-year follow-up) involving more recent implants, with modern articular couplings demonstrating low wear (such as ceramic-on-ceramic), and performed with minimally invasive technique and pre-operative CT-guided planning, would be desirable.

The aim of this study is to describe the survival rates and the long-term clinical and radiological outcome (minimum 10-year follow-up) of cementless THAs, with ceramic-on-ceramic couplings, performed with minimally-invasive technique and CT guided pre-operative planning, in post-traumatic osteoarthritis due to acetabular fractures

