### **Population**

retrospective, consecutive population treated with a cementless total hip arthroplasty with ceramic-on-ceramic bearing surfaces for post-traumatic hip osteoarthritis due to acetabular fracture. A minimum follow-up of 10 years was mandatory

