#### Inclusion criteria

- symptomatic, post-traumatic hip osteoarthritis due to acetabular fracture
- consecutive population with a minimum follow-up of 10 years
- cementless total hip arthroplasty with ceramic-on-ceramic bearing surfaces
- pre-operative planning using CT
- complete clinical and radiographic assessment

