#### Exclusion Criteria:

- other type of hip osteoarthritis
- other type of implants
- inadequate pre-operative planning (eg: no CT)
- incomplete assessment

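### Does the lack of a rule for cups revised before 10 years make the osseointegration result misleading?

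*Combined protocol and SAP*

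**What the plan says.** The Methods section sets a rule for reading a single cup: "Adequate osseointegration of the cup: at least 3 parameters out of 5". The signs listed make five if the two buttresses are counted separately. The section does not date the film, name a denominator, or say whether a replacement cup may be read.

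The clinical scores do have a time: "Clinical patient evaluation was assessed by using the HHS and WOMAC score at the minimum follow-up of 10 years". For radiology the time has to be taken from the aim in the Study description, which covers "the long-term clinical and radiological outcome (minimum 10-year follow-up) of cementless THAs".

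Three sections restrict entry. Population says "A minimum follow-up of 10 years was mandatory". The Inclusion criteria ask for a "consecutive population with a minimum follow-up of 10 years" and a "complete clinical and radiographic assessment". The Exclusion Criteria remove "incomplete assessment".

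Revision appears only in the Statistical analysis plan, where replacing any one component is the Kaplan-Meier end point. The Brief summary adds a complication rate, a failure rate and a descriptive account of the failures. No section links a revision to the radiographic reading.

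**The concern.** A cup revised for loosening has failed at exactly what the radiographic criterion measures. By 10 years that cup is gone, so there is no late film of it. The plan leaves three readings open: the hip drops out, the replacement cup is read, or the last film before revision is carried forward. Under the first, and under the second if the replacement reads as adequate, the fixation failure is not counted against osseointegration. The exclusion of incomplete assessments makes dropping out a natural reading.

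The radiographic result is part of the stated aim and the cohort is described as consecutive. A reader could therefore take the proportion as the result for every operated hip when it describes only cups still in place. The mean HHS and WOMAC raise the same question in milder form, mainly one of labelling.

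**Working it through.** The plan gives no osseointegration target, number of hips or event count, so it has no figure of its own to reproduce. The check is an illustration.

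**Inputs**
- R, share of hips revised by 10 years: 15% to 26% is the literature range in the Study description. It covers revision for any reason, and that section says the earlier studies often used outdated implants. A value of 5% is added as an assumption.
- f, share of revisions done for failed cup fixation: assumed. The documents give no loosening rate. The Study description cites dislocation (4.4%) and infection (5.6%), which can lead to revision of a well-fixed cup, so f may be low.
- p, share adequate among cups not revised for fixation: assumed 95%.

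**Step 1. Only cups revised for fixation drop out.** The reported proportion is p. With those cups counted as failures it is p(1 − R·f). The overstatement is p·R·f, in percentage points:

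| R | f = 0 | f = 10% | f = 25% | f = 75% |
|---|---|---|---|---|
| 5% | 0 | 0.5 | 1.2 | 3.6 |
| 15% | 0 | 1.4 | 3.6 | 10.7 |
| 26% | 0 | 2.5 | 6.2 | 18.5 |

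For example, 0.95 × 0.26 × 0.10 = 0.0247. The last column rests on an f for which the documents give no support.

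**Step 2. The other two readings.** If replacement cups are read and a share q of them is adequate, the overstatement is q·R·f. If the last film before revision is read and a share s of those is adequate, it is s·R·f. Each is zero when q or s is zero.

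**Step 3. All revised hips drop out, and those revised for other reasons had well-fixed cups.** With reported proportion p, the proportion over all operated hips is p(1 − R) + R(1 − f). At p = 85% and f = 10%:
- R = 15%: 0.85 × 0.85 + 0.15 × 0.90 = 0.8575, so the report is 0.75 points too low.
- R = 26%: 0.85 × 0.74 + 0.26 × 0.90 = 0.863, so the report is 1.3 points too low.

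The sign is therefore not fixed.

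**Step 4. Would a written rule do better?** The obvious rule readmits hips revised before 10 years, counts fixation failures as not osseointegrated, and uses cups with a known fixation outcome as the denominator. Unrevised patients who died or were lost before 10 years stay excluded.
- Suppose 10% of hips have fixation failure, 20% are unrevised but lost without a film, and p = 95% (all assumed). The rule gives 0.95 × 0.70 / 0.80 = 83.1%. Over all operated hips at the same p, the figure is 0.95 × 0.90 = 85.5%.
- Kaplan-Meier is affected too. With 15 of 100 hips revised and 25 unrevised losses excluded (both assumed), failure is 15/75 = 20%. With the 25 censored instead, it lies between 15% and 20%, depending on when they were lost.

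Such a rule can exchange a possible overstatement for an understatement.

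**The case for a change.** The best case for a change is that the omission is certain, the direction is likely, and the remedy is a few sentences using revision dates, components and reasons that the survival analysis and failure description need anyway. A per-cup threshold in a study with a radiographic aim does imply a proportion. Kaplan-Meier counts revision of any component, so it neither isolates cup fixation nor sets the denominator of that proportion.

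All of that stands as description. It does not show that the planned summary is wrong. Osseointegration among cups in place, shown beside implant survival and an account of the failures, is a sound and common way to describe such a cohort. Coding a revised cup as not osseointegrated answers a different question; it is a choice of estimand, not a correction. The suggested denominator of cups with a known fixation outcome is itself a selected subset, since it leaves out deaths, losses and cups removed for other reasons.

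One reservation remains. The reassurance assumes that revised hips stay in the cohort, as a planned failure rate and failure description imply. If the eligibility text were read as removing them altogether, the main damage would be to the survival estimate. That is a separate question of cohort selection.

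**Conclusion.** No change is needed. The plan leaves unwritten the reading time, the denominator and the label of a descriptive radiographic summary, and an analyst can fill these in sensibly: read the index cup and not its replacement, describe the result as applying to implants in place, and show the numbers revised, dead and lost beside it.

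The possible distortion has no known size. At 95% adequate and 10% of revisions for cup fixation (both assumed), it runs from about 0.5 points at an assumed 5% revision rate to 2.5 points at 26%. It is zero without fixation revisions, and about −0.75 to −1.3 points in the reverse case shown. The double-digit gaps need an unsupported f of 75%. The conclusion rests on revised hips being kept in the cohort and reported as failures, which the Brief summary and the Statistical analysis plan point to.

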### Statistical analysis plan

Statistical analysis has been done by using Windows SPSS 14.0, 14.0.1 version (SPSS Inc, Chicago, IL) and JMP, 12.0.1 version (SAS Institute Inc, Cary, NC, 1989-2007).

The quantitative data were expressed as average values and standard deviations, adding the range of minimum and maximum values. Statistical analysis was realized using Chi-squared test or Fisher exact test for qualitative data. Comparison of averages was performed using Student T test (significant correlation  $P<.05$ ).

The survival curves have been calculated and plotted according to Kaplan-Meier method. On x-axis time is expressed in years, while on y-axis the percentage of prosthesis survival is reported. The curve starts by definition at 100% survival when the period of follow-up begins. The implant is considered to be "surviving" up to when it was necessary to replace even single component. End point is the prosthesis failure. Prosthesis failure is defined as the revision of even one prosthetic component.

Each curve is flanked by a pair of curves symmetrical to it that are the 95% Confidence Interval. The range of the interval is closely dependent on the number of operations considered in the analysis. When the number of operations is low, uncertainty of analysis is high and showed by a wide confidence interval.

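### Symmetric 95% limits on the percentage scale have zero width before the first failure, exceed 100% after the first one to three failures, and give too high a lower limit when failures are few

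*Combined protocol and SAP*

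**What the plan says.** All the relevant wording on the interval is in the section Statistical analysis plan. The estimator is Kaplan-Meier, and for the plot "on y-axis the percentage of prosthesis survival is reported". The starting value is fixed: "The curve starts by definition at 100% survival when the period of follow-up begins". The limits are then described: "Each curve is flanked by a pair of curves symmetrical to it that are the 95% Confidence Interval". The section adds that "When the number of operations is low, uncertainty of analysis is high and showed by a wide confidence interval". The event is any revision: "Prosthesis failure is defined as the revision of even one prosthetic component".

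Neither that section nor the rest of the document names a variance formula, a transformation, a cap at 100%, or an exact or score method. No number of hips and no expected number of failures is given. Under Population, "A minimum follow-up of 10 years was mandatory". The Study description quotes a literature 10-year revision rate of 15% to 26%.

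**The concern.** Limits that lie symmetrically about a curve drawn in percent survival can only be the estimate plus and minus a multiple of its standard error. That interval works poorly near 100%, where every one of these curves begins. Three consequences follow.

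- Before the first failure the standard error is zero, so the band has no width however few hips there are. This does not fit the plan's own statement that a small number of operations appears as a wide interval.
- After the first few failures the upper limit is an impossible value.
- If failures stay few, the lower limit is too high, which is the direction that flatters the implant.

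Describing survival is a stated aim, and this band is the only measure of its uncertainty that the plan states. The Study description argues that low-wear implants and careful planning can improve long-term survival. A result with few failures is therefore the one hoped for, and it is where the interval performs worst.

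**Working it through.** **Inputs.** From the documents: 95% limits symmetric on the percentage scale, a start at 100%, at least 10 years of follow-up for every patient, and literature 10-year survival of 100 − 26 = 74% to 100 − 15 = 85%. Assumed: Greenwood variance, n = 20 to 100 hips, and a true survival of 95% as a low-failure case. The plan states no interval or sample size, so there is no figure to reproduce.

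**Reduction to the binomial.** With 10 years of follow-up mandatory there is no censoring before year 10. After k failures in n hips, S = 1 − k/n and the Greenwood SE is √[S(1 − S)/n].

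**Zero width.** At k = 0, S = 1 and SE = 0, so the limits are 100–100% for any n. The exact lower limit is 0.025^(1/n): 88.4% for n = 30 and 96.4% for n = 100.

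**Above 100%.** The upper limit exceeds 1 when 1.96 × √[S(1 − S)/n] > 1 − S. Squaring and simplifying gives k < 3.84 × (1 − k/n).
- k = 1 meets this for n ≥ 2, and k = 2 for n ≥ 5.
- For k = 3: 3 < 3.84 − 11.52/n, so n > 13.7, i.e. n ≥ 14.
- k = 4 never meets it without censoring, because 3.84 < 4.

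**Limits by number of failures (%).** Example for n = 30, k = 1: S = 0.9667, SE = √(0.9667 × 0.0333/30) = 0.0328, 1.96 × SE = 0.064, so 90.2 to 103.1.

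| n | Failures | Symmetric | Log-log | Exact (Clopper-Pearson) |
|---|---|---|---|---|
| 20 | 1 | 85.4–104.6 | 69.5–99.3 | 75.1–99.9 |
| 30 | 0 | 100–100 | no width | 88.4–100 |
| 30 | 1 | 90.2–103.1 | 78.6–99.5 | 82.8–99.9 |
| 30 | 2 | 84.4–102.3 | 75.9–98.3 | 77.9–99.2 |
| 30 | 3 | 79.3–100.7 | 72.1–96.7 | 73.5–97.9 |
| 100 | 1 | 97.0–101.0 | 93.1–99.9 | 94.6–100.0 |

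Against the exact limit at n = 30, the symmetric lower limit is too high by 7.4, 6.5 and 5.8 points after one, two and three failures (from unrounded limits).

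**How much of the curve is affected.** The expected time in the first 10 years with zero width or an upper limit above 100% is the integral over 0 to 10 years of P(0 to 3 failures by t), binomial. Constant hazard uses S(t) = S10^(t/10). The front-loaded case puts half of the failures evenly in years 0–2 and half evenly in years 2–10.

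| 10-year survival | Failure pattern | n = 30 | n = 60 | n = 100 |
|---|---|---|---|---|
| 85% | constant hazard | 7.5 y | 4.2 y | 2.5 y |
| 85% | front-loaded | 6.4 y | 2.4 y | 1.1 y |
| 74% | constant hazard | 4.6 y | 2.3 y | 1.35 y |
| 74% | front-loaded | 3.0 y | 1.0 y | 0.6 y |

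Of the 7.5 years, 2.0 have zero width and 5.4 have an upper limit above 100% (rounded separately).

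**Year-10 coverage of the symmetric interval** (exact binomial sums, nominal 95%).
- True survival 95%: 63.9% (n = 20), 78.2% (30), 86.8% (40), 80.6% (60), 87.7% (100).
- True survival 74, 80 or 85%: 90.5–95.1% for n = 30 to 100, but 81.9% at n = 20 and 85%.
- Chance that the lower limit lies above a true 85% (nominal 2.5%): 17.6% (n = 20), 4.8% (30), 4.9% (40), 4.2% (60), 5.5% (100).

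**Proposed interval.** Log-log limits, with the exact limit at zero failures, cover 92.5–97.8% in all 20 of these cases (four survival values by five sample sizes).

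**The case against.** **Zero width is not caused by symmetry.** It comes from Greenwood's variance being zero at S = 1, and log-log limits share it. This is correct. At 95% survival with n = 20 or 30, the lower limit misses in 35.8% and 21.5% of samples, which is exactly the chance of no failures, so log-log alone would not cure it. The exact limit at zero failures is therefore a necessary part of the change.

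**At the literature failure rate the year-10 result is little affected, and no test or threshold uses the limit.** This largely stands. The harm to the lower limit depends on few failures, and both 95% survival and n are assumptions. Coverage does jump with the true value, however. The 81.9% at n = 20 arises because the one-failure lower limit of 85.45% falls just above 85%; at a true 85.5%, coverage is 95.2%. In the other direction, at n = 30 coverage falls to 85.5% within the 74–85% range.

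**Capping at 100% would remove the impossible values.** It would, but the plan does not state it, it would break the stated symmetry, and it leaves the zero width and the high lower limit as they are.

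**"Symmetrical" may be loose wording.** If so, the plan misdescribes its method and the same sentence needs replacing.

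**The replacement is imperfect and not the only choice.** This stands as a caveat. At 95% survival its upper limit falls below the truth in 7.5% (n = 20) and 6.1% (n = 30) of samples, against 2.5% nominal. With few failures its lower limit is below the exact one (78.6% against 82.8% at n = 30, one failure). Wilson or Clopper-Pearson limits would also serve up to year 10.

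**Conclusion.** The concern holds and should be fixed. As written, the interval has no width before the first failure and, with 14 or more hips and no censoring, passes 100% after each of the first three failures. Neither result depends on the true failure rate. The lower-limit problem is conditional: it is material if failures are few by year 10 (90.2% reported against 82.8% exact with one failure in 30 hips) and smaller at the literature rate. The Kaplan-Meier estimate itself is not affected.

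The conclusion rests on reading the symmetry as applying to the plotted percentage scale, on Greenwood variance, and on no censoring before year 10. The sizes also rest on the assumed 20 to 100 hips.

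**What to change.** Replace the sentence on symmetrical limits with: *Pointwise 95% confidence intervals use the complementary log-log transformation of the Kaplan-Meier estimate with Greenwood variance; at times when no failure has occurred, the exact binomial lower limit is given, based on the number of hips still at risk at that time.* Print the numbers at risk under the curve.

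The denominator matters after year 10, when censoring begins. With no failures the exact lower limit 0.025^(1/m) is 88.4% with m = 30 at risk, 83.2% with 20 and 69.2% with 10.

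The cost is one sentence, and possibly a calculation outside the software's default output. No new data are needed. The reported lower limit will be less favourable, and the upper limit misses somewhat more often than nominal in small cohorts with few failures.
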